**Colitis/Ileus**

Cases of colitis complicated by ulceration, bleeding, ileus, and infection have been observed. Patients experiencing ileus should receive prompt antibiotic support.

**Thromboembolism**

Thromboembolic events have been observed in patients receiving irinotecan-containing regimens; the specific cause of these events has not been determined.

**Pregnancy**

The pregnancy category of irinotecan is D. Women of childbearing potential should be advised to avoid becoming pregnant while receiving treatment with irinotecan. If a pregnancy is reported, treatment should be discontinued. The patient should be withdrawn from the study, and the pregnancy should be followed until the outcome becomes known.

**Patients at Particular Risk**

In clinical trials of the weekly schedule of irinotecan, it has been noted that patients with modestly elevated baseline serum total bilirubin levels (1.0 to 2.0 mg/dL) have had a significantly greater likelihood of experiencing first-cycle grade 3 or 4 neutropenia than those with bilirubin levels that were less than 1.0 mg/dL (50.0% [19/38] versus 17.7% [47/226];  $p < 0.001$ ). Patients with abnormal glucuronidation of bilirubin, such as those with Gilbert's syndrome, may also be at greater risk of myelosuppression when receiving therapy with irinotecan.

**Acute Infusion Associated Reactions**

Acute infusion-associated reactions characterized by flushing, shortness of breath, facial swelling, headache, chills, back pain, tightness of chest or throat, and hypotension have been reported in a small number of patients treated with liposome drugs. In most patients, these reactions generally resolve within 24 hours after the infusion is terminated. In some patients, the reaction resolves by slowing the rate of infusion. Most patients who experienced acute infusion reactions to liposome drugs are able to tolerate further infusions without complications.

**Other Anticancer Therapies**

Subjects will be treated with one or more of the following approved therapies:

- 5-FU
- Leucovorin
- oxaliplatin

### **Description of Combination Therapies**

A description of each anticancer therapy to be used in combination with nal-IRI is described below. Please also refer to the package inserts for more details.

### **Storage and Handling of Combination Therapies**

Refer to the country specific package inserts for details on storage and handling for 5-FU and leucovorin, and oxaliplatin,

### **Packaging and Labeling of Combination Therapies**

Commercially available 5-FU and leucovorin (l + d racemic form, or the levoleucovorin l form) and oxaliplatin will be administered in accordance with the specific treatment regimen and package inserts.

### **Potential Toxicities of Combination Therapies**

#### **Potential Toxicities with 5-FU**

Stomatitis and esophagopharyngitis (which may lead to sloughing and ulceration), diarrhea, anorexia, nausea, emesis and leukopenia are commonly seen with treatment; alopecia and dermatitis, in the form of pruritic rash usually appearing on the extremities, may also be seen (see US package insert). Common adverse events ( $\geq 20\%$ ) that were observed with nal- IRI in combination with 5-FU/LV in clinical trials considered to be related were: diarrhea, nausea, vomiting, decreased appetite, neutropenia, fatigue, anemia, stomatitis and pyrexia.

#### **Potential Toxicities with Oxaliplatin**

The following adverse events are relatively common ( $\geq 40\%$ ) with oxaliplatin treatment in combination with 5-FU/LV and are to be expected with the nal-IRI-containing regimen: peripheral sensory neuropathy, neutropenia, thrombocytopenia, anemia, nausea, increases in transaminases and alkaline phosphatase, diarrhea, fatigue, emesis, and stomatitis. In a phase 3 study of the FOLFIRINOX regimen (5-FU/LV + irinotecan + oxaliplatin), the most common ( $> 5\%$ ) Grade 3-4 adverse events were: neutropenia, fatigue, vomiting, diarrhea, thrombocytopenia, sensory neuropathy, anemia, elevated alanine aminotransferase (ALT) level, thromboembolism, and febrile neutropenia, Grade  $\frac{3}{4}$  hypersensitivity reactions, including anaphylactic reactions, have been observed in 2-3% of colon cancer patients receiving oxaliplatin; see package insert for more information.

## 11. ADVERSE EVENTS

### 11.1 Definitions

#### 11.1.1 Adverse Event

The term “adverse event” (AE) includes any sign, symptom, syndrome, or illness that appears or worsens in a subject during the period of observation in the clinical study and that may impair the wellbeing of the subject. The term also covers laboratory findings or results of other diagnostic procedures that are considered to be clinically significant (*e.g.*, that requires unscheduled diagnostic procedures or treatment measures, or result in withdrawal from the study). An AE is therefore any unfavorable and unintended symptom or disease temporally associated with the administration of an investigational product, whether or not related to that investigational product.

The adverse event may be:

- A new illness/condition;
- Worsening of a sign or symptom of the condition under treatment, or of a concomitant illness/condition;
- An effect of the study drug; or
- A combination of 2 or more of these factors.

No causal relationship with the study drug or with the clinical study itself is implied by the use of the term “adverse event.”

The Investigator will probe, via discussion with the subject, for the occurrence of Aes during each subject visit and record the information in the site’s source documents. Aes will be recorded in the subject CRF. Aes will be described by duration (start and stop dates and times), severity, outcome, treatment and relation to study drug, or if unrelated, the cause.

Surgical procedures themselves are not adverse events; they are therapeutic measures for conditions that require surgery. The condition(s) for which the surgery is required may be an adverse event. Planned surgical measures permitted by the clinical study protocol and the condition(s) leading to these measures are not adverse events.

When a clear diagnosis is available that explains the abnormal objective findings, this diagnosis will be recorded as an adverse event and not the abnormal objective findings (*e.g.*, viral hepatitis will be recorded as the adverse event and not the transaminase elevation). If a definitive diagnosis is not available, then the sign(s) (*e.g.*, clinically significant elevation of transaminase levels) or symptom(s) (*e.g.*, abdominal pain) will be recorded as the adverse event.

Adverse events fall into the categories “serious” and “non-serious.”

#### 11.1.2 Serious Adverse Event

A serious adverse event is one that at any dose of the study drug or at any time during the period of observation:

- Results in death
- Is life-threatening (defined as an event in which the subject was at risk of death at the time of the event; it does not refer to an event which hypothetically might have caused death if it were more severe)
- Requires inpatient hospitalization or causes prolongation of existing hospitalization (see note below for exceptions)
- Results in persistent or significant disability/incapacity
- Is a congenital anomaly/birth defect
- Is an important medical event, defined as a medical event that may not be immediately life-threatening or result in death or hospitalization but, based on appropriate medical and scientific judgment, may jeopardize the subject or may require intervention (e.g., medical, surgical) to prevent one of the other serious outcomes listed above. Examples of such events include but are not limited to intensive treatment in an emergency department or at home for allergic bronchospasm; blood dyscrasias or convulsions that do not result in hospitalization. “Medically important” should be marked only if no other serious criteria are met.

An “unexpected SAE” is any SAE for which the nature, specificity or severity is not consistent with the currently known adverse event profile of the investigational agent(s).

**NOTE:** The following hospitalizations are not considered SAEs in UFHCC clinical studies:

- a visit to the emergency room or other hospital department lasting less than 24 hours that does not result in admission (unless considered an “important medical event” or a life-threatening event)
- elective surgery planned before signing consent
- admissions as per protocol for a planned medical/surgical procedure
- routine health assessment requiring admission for baseline/trending of health status (e.g., routine colonoscopy)
- medical/surgical admission for purpose other than remedying ill health state that was planned before study entry. Appropriate documentation is required in these cases.
- admission encountered for another life circumstance that carries no bearing on health status and requires no medical/surgical intervention (e.g., lack of housing, economic inadequacy, caregiver respite, family circumstances, administrative).

### **Clarification of the difference in meaning between “severe” and “serious”**

The term “severe” is often used to describe the intensity (severity) of a specific event (as in mild, moderate, or severe myocardial infarction); the event itself, however, may be of relatively minor medical significance (such as severe headache). Any grade  $\geq 3$  adverse event per CTCAE is generally considered severe AE. This is not the same as “serious,” which is based on the outcome or action criteria usually associated with events that pose a threat to life or functioning. Seriousness (not severity) serves as a guide for defining regulatory reporting obligations.

#### 11.1.3 Non-Serious Adverse Event

A non-serious adverse event is any adverse event not meeting any of the serious adverse event

criteria.

### 11.2 Period of Observation

Following the subject's written consent to participate in the study, all SAEs must be collected, including those thought to be associated with protocol-specified procedures. Collection of all SAEs must continue until the post-op visit (or pre-op visit if the subject does not proceed with surgery). If applicable, SAEs must be collected that relate to any later protocol-specified procedure (e.g., protocol-specified resection surgery). SAEs not related to a later protocol-specified procedure will not be collected beyond 30 days post last dose of study treatment. The investigator should notify the DISC of any SAE occurring after this time period that is believed to be related to the investigational product or protocol-specified procedure.

The investigator will begin collecting non-serious adverse event (NSAE) information once administration of the investigational product is initiated. This NSAE information should also be collected from the start of a placebo lead-in period or other observational period intended to establish a baseline status for the subjects. Treated subjects, including those who were prematurely discontinued from the study, will be followed for any adverse events that occur during the study until the post-op visit (or pre-op visit if the subject does not proceed with surgery). However, after 30 days post last dose of study treatment, only unexpected AEs related to a protocol-specified procedure (e.g. resection surgery and associated hospitalization) will be reported. If another course of anti-cancer therapy is initiated prior to the that follow-up period visit, collection of adverse events will no longer be performed, with the exception of events that may be possibly, probably, or definitely related to the investigational agent or are clinically significant.

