### 12.2 Analysis of Primary Endpoint

The primary analysis will use the modified Intention-to-Treat (mITT) population consisting of subjects who are enrolled and received any dose of study medication. The mITT population will be included in summary tables of subject demographics and disease characteristics, and in analysis of efficacy. Subjects who did not progress to surgery (for any reason) or are lost to follow-up will be censored at the day of their last objective tumor assessment and will be unevaluable for the primary endpoint. Subjects failing to proceed to surgery will be replaced, but all will support the secondary endpoints including feasibility, safety and correlative biologic analyses.

Post-operative complications will be measured at the EOT visit 4-6 weeks after surgery. Complications occurring within 30 days after surgery and contributing to the primary endpoint are defined as hospital re-admission, death, second surgery or interventional procedure or major complications extending hospital stay. The proportion and its exact 90% confidence interval of 30-day post-operative complication rate will be calculated. Statistical analyses will be conducted using SAS v9.4 (SAS institute, Cary, NC).

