| 
8) Submission of initial tumor specimen (FFPE) obtained prior to enrollment as part of diagnostic workup, as well as tumor tissue at the time of surgical resection, are both required for this study. In the event a FFPE block is not available at study entry, slides or cytology specimens may be acceptance with permission from the study PI.
 
9) Subjects will be followed for overall survival approximately every 6 months for 5 years after this visit.
 
10) Adverse Events and Concomitant Medications are to be collected in accordance with sections 11.2 and 7.2.2 of this protocol, respectively.
 
11) Microbiome samples will be collected up to 5 timepoints: enrollment, after 4 cycles, at completion of chemotherapy, after completion of radiation if applicable, and at post-surgical EOT. There will be no reportable protocol deviation for microbiome specimens not collected or collected outside of collection window. Such variance poses no risk to patient safety or primary study endpoints.
 
12) ECGs will be done at baseline and as medically indicated
 |
|--|

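### Section 11.2 contradicts itself on post-operative event collection and does not match the 30-day primary endpoint, so endpoint events can be missed, and any loss favours success

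*Combined protocol and SAP*

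**What the plan says.** **Endpoint.** Section 12.2 counts these events within 30 days of surgery: "hospital re-admission, death, second surgery or interventional procedure or major complications extending hospital stay". Section 2.1 gives the same list. Neither attaches a test of relatedness, expectedness or seriousness. On timing, section 12.2 says: "Post-operative complications will be measured at the EOT visit 4-6 weeks after surgery".

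**Collection.** Section 11.2 gives two rules for SAEs. The first is unrestricted: "Collection of all SAEs must continue until the post-op visit" (or the pre-operative visit if there is no surgery). The second restricts by relatedness: "SAEs not related to a later protocol-specified procedure will not be collected beyond 30 days post last dose of study treatment". Its paragraph on non-serious events follows patients to the post-operative visit, but adds that beyond 30 days after the last dose "only unexpected AEs related to a protocol-specified procedure (e.g. resection surgery and associated hospitalization) will be reported".

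**Schedule.** Section 6.4 lists history, examination, laboratory tests, pathology, specimens and FACT-G at the end-of-treatment (EOT) visit. It has no complication or re-admission item. Appendix A schedules an adverse event review there, and its footnote 10 says: "Adverse Events and Concomitant Medications are to be collected in accordance with sections 11.2 and 7.2.2 of this protocol, respectively".

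**Safety analysis.** Section 12.5 has patients assessed for AEs to the later of 30 days after the last dose and 30 days after surgery. The same section leaves AEs more than 30 days after the last dose out of the safety analysis.

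**Timing of surgery.** Section 7.1 places resection 4 to 8 weeks after the last dose. Section 7.2.4 counts the same interval from the end of radiotherapy when that is given.

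**The concern.** The endpoint includes events of any cause, while one of the two collection rules stops at events attributed to the procedure. A site that follows the restrictive sentences would not collect a serious event in the third post-operative week if it is judged due to the underlying disease. It would not report an outpatient intervention for a recognised surgical complication if the event is classed as non-serious and expected. Both count under section 12.2.

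The error runs one way. A complicated patient who is not recorded becomes a success, and the result is judged against a fixed 30% rate with no control arm to share the loss. The relatedness judgement is made by an investigator in an open-label trial. With so few patients, one event can decide the conclusion.

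**Working it through.** **1. How much of the endpoint window lies under the restriction.** The last dose is day 0, surgery falls on day 28 to 56, and unrestricted collection ends on day 30.
- Surgery on day 28: post-operative days 1 and 2 are days 29 and 30, so 2 of the 30 days are unrestricted.
- Surgery on day 29: 1 of 30.
- Surgery on day 30 or later: 0 of 30.

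After radiotherapy, surgery comes later still. On the restrictive reading, at least 28 of the 30 days are covered by the limit, and usually all 30.

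**2. Visit timing.** Four to six weeks is day 28 to 42. A visit on day 28 cannot see days 29 and 30, and one on day 29 cannot see day 30. The other 13 of the 15 permitted days fall at or after day 30.

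**3. The plan's own figure.** Section 12.1 gives 25 patients, 30% against 10%, a one-sided exact test at 0.05 and power of about 80%. Find the largest c with P(X ≤ c | 25, 0.30) ≤ 0.05:
- c = 3: type I error 0.033, power P(X ≤ 3 | 25, 0.10) = 0.764.
- c = 4: type I error 0.090, which is too large.

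The exact test gives 76.4%. A normal approximation with the null standard error gives 79.4%, close to the stated figure. This gap is a separate matter and does not affect the point here. The plan states no success count; 3 or fewer is derived. If 28 patients are evaluable, as section 4.1 says, the cutoff is 4 or fewer, with type I error 0.047 and power 0.858.

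**4. Effect of missed patients.** Let m be the share of complicated patients not recorded at all. The recorded rate at a true 30% is 0.30 × (1 − m), and false success is P(X ≤ c) at that rate. The documents give no value for m, so the range is an assumption.

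| m (assumed) | recorded rate | n = 25, c = 3 | n = 28, c = 4 |
|---|---|---|---|
| 0 | 0.300 | 3.3% | 4.7% |
| 5% | 0.285 | 4.7% | 6.6% |
| 10% | 0.270 | 6.4% | 9.1% |
| 20% | 0.240 | 11.7% | 16.3% |
| 30% | 0.210 | 19.9% | 27.1% |

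Visit timing alone is a small part of this. If every patient were seen on day 28 and events were uniform over 30 days, m would be 2/30 = 6.7% and false success at n = 25 would be 5.2%. Both conditions are extreme.

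**5. One event at the boundary.** Section 12.2 reports an exact 90% interval. With 4 of 25 its upper limit is 0.330, which includes 30%. With 3 of 25 it is 0.282, which excludes it. If exactly one complicated patient were always missed, false success would be P(X ≤ 4 | 25, 0.30) = 9.0%, or P(X ≤ 5 | 28, 0.30) = 11.3% with 28 patients.

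**The case against.** A reader might infer that the adverse event review is the only scheduled capture of complications. The documents do not support that. Section 12.2 sets its own measurement at the EOT visit and does not route it through AE reporting. Section 6.4 schedules an interim history and examination there with no restriction, which could elicit a re-admission or procedure. Section 6.5 survival follow-up would reveal deaths. Section 15.7 promises study-specific case report forms, which are not among the documents, so a complication page may exist.

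Nor is the restriction the settled rule. The other sentence in section 11.2 asks for all SAEs to the post-operative visit, and under section 11.1.2 death, hospitalisation and prolonged stay are SAEs. The expectedness limit sits in the paragraph on non-serious events, so serious procedure-related complications are collected on either reading. Late SAEs believed related to the drug or procedure must still be notified to the DISC. Section 12.5 extends AE assessment to 30 days after surgery, which covers days 29 and 30. Appendix I says section 11.2 was revised to capture surgical complications, which points to an intent opposite to loss.

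All of this narrows the point without removing it. The history is not tied to an endpoint record. Survival follow-up does not find re-admissions or procedures. Notifying the DISC is not the same as recording an endpoint. Section 12.5 conflicts with the stopping rules in section 11.2, and the one event-review item that Appendix A schedules at the visit points to section 11.2.

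**Conclusion.** The point holds as an inconsistency that exposes the primary endpoint to loss. Section 11.2 contradicts itself, and its restrictive sentences match neither the endpoint in sections 2.1 and 12.2 nor the post-operative window in section 12.5. No complication item is named at the EOT visit, and that visit may precede day 30. The exposed events are those judged unrelated to the resection, and those both non-serious and expected.

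It is tempting to conclude that complications will be under-counted, or that the type I error is 6.4% or 11.7%. The documents support neither. Those percentages illustrate missed shares of 10% and 20%, which are assumptions, with 25 evaluable patients and a derived cutoff of 3. The direction is certain, since a missed event can only favour success, but the size is unknown. The written rule still needs correcting, because sites could follow it in good faith and one event can settle the result.

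**What to change.** - Reconcile sections 11.2, 12.2 and 12.5 so that, from surgery through post-operative day 30, every endpoint component is recorded regardless of relatedness, expectedness or seriousness. The limits tied to 30 days after the last dose should not apply to these events in that period.
- Add a named 30-day complication item or form to section 6.4 and Appendix A, and state that the section 12.2 analysis draws on it.
- Ascertain endpoint status at or after day 30. If the visit falls on day 28 or 29, complete it by chart review or a telephone call.

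The cost is protocol wording, one case report form page and an occasional short contact. The surgical record should already hold most of the data. The downside is a few more events to record and possibly a higher observed complication rate.

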#### Overall treatment plan

- ONIVYDE® with 5-fluorouracil, leucovorin and oxaliplatin (NALIRIFOX) at the recommended for phase II doses determined from NCT02551991-IV dosing every 2 weeks x 8 total treatments (4 months)
- Surgical resection in the absence of documented progression within 4-8 weeks following last dose of therapy. Clinical response assessment following last cycle of NALIRIFOX.
- Optional chemoradiotherapy with evidence of local disease progression or as otherwise defined in Section 7.2.4
- Optimal supportive care and growth factor support per recommendations from NCT02551991
- Clinical follow-up 4-6 weeks post-operatively (EOT visit)
- Survival follow-up every 6 months for 5 years and documentation of any recurrence.

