#### 12.6 Enhanced AE Safety Monitoring

When accrual is greater than 10 subjects, if at any time, 5 of the initial 10 treated subjects or 50% or more of all treated subjects have experienced a non-hematologic grade  $\geq$  3,4, 5 adverse event considered at least possibly related to treatment (possible, probable, or

definite), accrual will be temporarily suspended to this study for a review by the PI and the Data Integrity and Safety Committee. Grade 4 and 5 adverse events deemed “unrelated” or “unlikely to be related” will be reviewed and monitored, to assess for the emergence of a previously unrecognized treatment-related adverse event.

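### From day 31 after the last dose, Section 11.2 no longer reports new non-serious drug-related AEs, and Section 12.5 contradicts both 11.2 and itself on late AEs

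*Combined protocol and SAP*

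**What the plan says.** Section 11.2 sets three rules for AEs in treated subjects.

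- General rule: subjects "will be followed for any adverse events that occur during the study until the post-op visit (or pre-op visit if the subject does not proceed" to an operation).
- Day-30 limit, in the sentence that follows: "after 30 days post last dose of study treatment, only unexpected AEs related to a protocol-specified procedure" are reported. Drug-related non-serious events are not excepted.
- Another anti-cancer therapy: once one starts, AE collection stops, "with the exception of events that may be possibly, probably, or definitely related to the investigational agent or are clinically significant". No day limit is attached to this exception.

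Serious events have their own route in the same section: "The investigator should notify the DISC of any SAE occurring after this time period that is believed to be related to the investigational product" or to a protocol procedure.

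The timetable comes from the overall treatment plan in Section 7.1: "Surgical resection in the absence of documented progression within 4-8 weeks following last dose of therapy", then "Clinical follow-up 4-6 weeks post-operatively (EOT visit"). Appendix A schedules AE review at the pre-surgical and post-op visits, but footnote 10 refers back to 11.2 for what is collected.

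Section 12.5 has patients assessed for AEs to 30 days after the last dose or 30 days after surgery, whichever is later. The same section leaves AEs arising more than 30 days after the last dose out of the safety analysis.

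Section 12.6 suspends accrual for review "if at any time, 5 of the initial 10 treated subjects or 50% or more of all treated subjects" have had a non-hematologic AE of grade 3 or higher that is at least possibly related. It does not require the event to be serious, and it gives no onset window.

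**The concern.** The primary objective (Section 2.1) is the safety and feasibility of the regimen before surgery. The weeks between the last dose and the operation are when lingering toxicity can decide whether a subject reaches surgery. Section 10.1.8 names toxicities of oxaliplatin with 5-FU/LV that "are to be expected with the nal-IRI-containing regimen: peripheral sensory neuropathy" is first on the list. An event of that kind fails both day-30 conditions: it is neither unexpected nor caused by a procedure. If it is new after day 30 and not serious, 11.2 gives no instruction to report it.

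Three things are at stake. The safety tables may understate late toxicity. A subject who misses surgery because of such an event is unevaluable for the primary endpoint and is replaced (Section 12.2), possibly without a graded, attributed AE record of the cause. The 12.6 count may also miss a qualifying event.

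**Working it through.** The plan gives no figure to reproduce here. The check is date arithmetic, with the last dose as day 0, and then a comparison of sections.

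**Inputs.** Last dose to surgery is 4-8 weeks, so days 28-56 (Section 7.1). Surgery to the post-op visit is 4-6 weeks, so 28-42 days (Section 7.1). The 11.2 limit applies from day 31.

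**Window without radiotherapy**
- Post-op visit: 28 + 28 = day 56 at the earliest; 56 + 42 = day 98 at the latest.
- Restricted time up to that visit: 56 - 30 = 26 days to 98 - 30 = 68 days. As a share of calendar time since the last dose: 26/56 = 46% to 68/98 = 69%.
- Part before surgery: none if surgery is on days 28-30; at most 56 - 30 = 26 days.
- The pre-surgical part is always the smaller one. Its largest share is with surgery on day 56 and the visit on day 84: 26/(84 - 30) = 26/54 = 48%.

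**Window with radiotherapy.** Section 7.2.4 puts surgery 4-8 weeks after radiotherapy ends. Its final dose of 50.4-54 Gy at 1.8 Gy per fraction is 28-30 fractions. Assuming five fractions a week (not stated in the plan), that takes 28/5 × 7 = 39 to 30/5 × 7 = 42 days. Even if it began on day 0, surgery would fall on days 39 + 28 = 67 to 42 + 56 = 98, leaving 37 to 68 restricted pre-surgical days. A later start adds to this. The shorter schedules that 7.2.4 also allows would reduce it.

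**Section 12.5 against itself and 11.2**
- Assessment ends 30 days after surgery: 28 + 30 = day 58 to 56 + 30 = day 86.
- Analysis stops at day 30, so 28 to 56 days are assessed and then excluded.
- With surgery no earlier than day 28, the exclusion also removes nearly all the procedure-related AEs that 11.2 does collect.
- The end dates differ: day 56-98 under 11.2 and day 58-86 under 12.5.

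**What other text covers after day 30**

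| Event | Covered? |
|---|---|
| Related SAE | Yes, notified to the DISC (11.2) |
| AE already present | Followed to outcome (11.3) |
| Laboratory toxicity | Largely: CBC and metabolic panel at both later visits (6.3, 6.4) |
| Reason for withdrawal | CRF description (8.2), not a graded, attributed AE |
| New, symptomatic, non-serious, drug-related AE | No reporting instruction |

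Section 11.1.2 separates severity from seriousness, so a grade 3 event can fall in the last row.

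**Section 12.6.** A late event matters to the count only if that subject had no earlier qualifying event. In that case one unreported event can separate 4 of 10 from 5 of 10.

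**The case against.** A 30-day post-dose cut-off appears for SAEs in 11.2 and again in 12.5, so it looks deliberate, and moving it could be called preference. That is fair as far as it goes. However, Appendix I gives the purpose of the late-AE change as capturing complications of surgery and records no decision to drop drug toxicity. Nor does a deliberate cut-off explain why 12.5 assesses AEs that it then excludes.

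Four stronger readings are tempting, and the documents do not support them.

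- **Late drug toxicity is definitely kept for subjects on another therapy and dropped for those going straight to surgery.** The day-30 limit is written for all treated subjects. The final sentence of 11.2 can be read in order, as preserving drug-related events only when new therapy starts inside the 30 days. On a literal reading ascertainment does differ by subsequent therapy, but the text does not settle which reading applies. Either way, 12.5 excludes late events for everyone, and this single-arm trial plans no comparison by later therapy.
- **46-69% of the toxicity is lost.** Those are shares of calendar time, more than half of the restricted time is post-operative, and attribution there is confounded by surgery. No onset distribution is given.
- **12.6 demands these events because it applies at any time.** That phrase says when the threshold may be crossed; it does not set an onset window. The consequence is a temporary pause for review.
- **The events are covered nowhere.** The general rule in 11.2 and the assessment sentence in 12.5 do reach them. An investigator might also class a toxicity that prevents resection as an important medical event, and so as serious. The accurate statement is that the plan gives conflicting instructions, and the specific reporting sentence excludes these events.

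**Conclusion.** The point holds in limited form. As written, 11.2 makes new non-serious drug-related AEs unreportable from day 31 after the last dose, in all subjects. Without radiotherapy this affects 0-26 days before surgery and 26-68 days up to the post-op visit; radiotherapy lengthens it. The firmest defect is in 12.5, which assesses AEs for 28-56 days that it then excludes from analysis. Whether ascertainment also differs by subsequent therapy depends on an ambiguous sentence in 11.2 that needs clarifying.

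This assumes that subjects keep to the 4-8 and 4-6 week windows and that the day-30 sentence overrides the general rule before it. The number of events lost cannot be stated from the documents. Priority is minor to moderate.

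**What to change.** Reconcile the three sections.

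- **11.2:** state that AEs at least possibly related to any agent of the regimen, as well as procedure-related AEs, are reported until the post-op visit (pre-op visit if there is no surgery), whether or not another therapy has started. This also resolves the ambiguous last sentence.
- **12.5:** remove the 30-day exclusion for these events, use the same end date as 11.2, and tabulate related AEs with onset after day 30 separately so that the on-treatment summary stays readable.
- **12.6:** state that qualifying events with onset after day 30 count toward the threshold.

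The cost is amendment wording, a few more CRF entries and a slightly higher reported toxicity rate. Appendix A already schedules AE review at both later visits, so no visit is added. In subjects without surgery, events after the pre-op visit would still fall outside collection.
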